8.2 Confirmation of Eligibility

All screening assessments and relevant medical history must be available and reviewed by the investigator before eligibility can be confirmed. Eligibility waivers will not be granted. After the investigator determines that a patient is eligible, study site personnel will complete an enrollment authorization form to be sent to the medical monitor for review/approval. Written authorization by the medical monitor is required before a patient can be officially enrolled and begin study treatment.

8.3 Medical and Leukemia History

Clinically significant medical and surgical history not pertaining to the underlying malignancy under study that started prior to informed consent will be collected. "Clinically significant" is generally regarded as any diagnosis requiring on-going treatment intervention and follow-up. Signs and symptoms of concurrent medical conditions must be adequately documented at Screening in order to establish baseline severities. Clinically relevant prior and current medical and surgical history will be reported on the Medical and Surgical History eCRF.

Smoking history (never smoker; former smoker; current smoker) will also be recorded.

The following details minimally regarding the diagnosis of AML will be collected and recorded on the eCRF: age and date of diagnosis (month, day, year); AML subtype (*de novo*; AML with myelodysplasia-related changes; therapy associated AML); history of myelodysplastic or myeloproliferative (eg, chronic myelomonocytic leukemia [CMML]) syndrome; history of prior exposure to leukemogenic agents (eg. alkylating agents, topoisomerase II inhibitors); cytogenetic abnormalities identified by conventional cytogenetic testing and/or FISH; CBC with differential; percent leukemic blasts (peripheral blood and bone marrow); *NPM1* mutation subtype (A, B, D, other); *FLT-3* mutational status (wild-type; internal tandem duplication [ITD] mutation, tyrosine kinase domain [TKD] mutation, or both).

8.4 Study Medication Dispensation

During periods of hospitalization, study medication (ENTO or placebo) will be dispensed by the in-patient pharmacy and administered by in-patient medical/nursing staff. Study medication for

CONFIDENTIAL

Protocol KB-ENTO-3001 v4.0

(Amendment 3.0)

outpatient use will be dispensed by study center personnel to ensure adequate drug supply for home administration throughout the treatment phase in accordance with details outlined in the Pharmacy Manual. Instructions will be provided to subjects for dosing, storage, and disposition of unused study drug.

8.5 Efficacy Assessments

Assessments that define the quality of response to study treatment will include physical examination, peripheral blood counts, and bone marrow examination. All assessments of response will be made by the investigator in accordance with ELN 2017 criteria ([Döhner 2017](#)) with minor modification for neutrophil and platelet count thresholds that define CR per the International Working Group (IWG) criteria ([Cheson 2003](#)). See [Appendix 4](#) for criteria that define each response category.

8.5.1 Bone Marrow Examination

A bone marrow aspirate will be performed at Screening (within 14 days before the first administration of study treatment) for confirmation of diagnosis, morphology (spicule prep), cytogenetics/FISH and *NPM1* and *FLT3* mutational status. **In cases in which an adequate bone marrow aspirate cannot be obtained at Screening (eg, due to dry tap, hypocellularity or hemodilution), a trephine bone marrow biopsy is mandated.** Bone marrow aspirates are required in Induction Cycle 1 (up to but no later than Day 42) and again post-Chemotherapy Cycle 2 (no later than Day 42) to assess remission status. Thereafter, perform bone marrow examination for confirmation of suspected leukemic relapse.

Additional biomarker assessments including (but not limited to) the presence of other somatic mutations at each of the aforementioned timepoints will be conducted (see [Section 8.8](#)).

8.5.2 Measurable Residual Disease

NPM1-m MRD assessments on peripheral blood and bone marrow aspirate will be conducted in a central laboratory post-Chemotherapy Cycle 2 for subjects in CR, no later than Day 42. Additionally, *NPM1*-m will be assessed as part of a broader panel of AML somatic mutations on peripheral blood only at End of Study Treatment, and every 3 months during long term follow-up in subjects who achieve MRD negative CR post-Chemotherapy Cycle 2, until morphologic relapse.

8.6 Safety Assessments

8.6.1 Physical Examination and Vital Signs

A complete physical examination that includes a neurological exam must be performed at Screening. Thereafter, a targeted physical exam may be performed at each of the designated time points in [Table 7](#). Height and weight will be measured at Screening. Only weight will be measured thereafter at designated time points.

CONFIDENTIAL

Protocol KB-ENTO-3001 v4.0

(Amendment 3.0)

Vital signs include measurement of blood pressure, respiratory rate, pulse, temperature, and percent oxygen saturation by pulse oximetry. After discharge from hospital, assess vital signs at each of the designated time points indicated in [Table 7](#).

Blood pressure and pulse should be measured at least 5 minutes after rest in a quiet setting without distractions. To the extent possible, measure vital signs prior to blood collection for laboratory assessments.

Subjects \geq 60 years of age or those with impaired renal function receiving cytarabine at doses specified in this study are at risk for cerebellar toxicity. Monitor for the occurrence of nystagmus, slurred speech, or dysmetria on each day of cytarabine dosing during induction and consolidation. Follow dose modification guidelines outlined in [Section 6.5.2](#) or those consistent with institutional care standards in the setting of neurotoxicity.

8.6.2 ECG

A triplicate, 12-lead ECG will be obtained as outlined in [Table 7](#). ECG is required at Screening and thereafter as clinically indicated during treatment.

8.6.3 Echocardiography/Multi-gated Acquisition Scan

An echocardiogram (ECHO) or multigated acquisition (MUGA) scan must be performed at Screening and at the End-of-Treatment Visit. For subjects receiving anthracycline in Induction Cycle 2, consider repeating an ECHO or MUGA scan within 48 hours prior to Cycle 2, Day 1 in subjects at increased risk for cardiotoxicity.

8.6.4 Laboratory Assessments

See [Table 7](#) for the list of clinical laboratory tests to be performed and their timing and frequency.

The investigator must review results for protocol-specified laboratory assessments, document his/her review, and record any clinically significant changes from baseline, defined as the value most proximate to initiation of study treatment, as an AE. If laboratory abnormalities from non-protocol specified laboratory tests require a change in subject management or are considered clinically significant (eg, requiring treatment modification), these must also be recorded as an AE. Laboratory reports must be filed with the source documents.

Abnormal laboratory findings associated with the underlying disease are not considered clinically significant unless judged by the investigator to be more severe than expected for the underlying condition. Clinically significant laboratory abnormalities should be reassessed during the study, up to 30 days after the last dose of study treatment until the results return to normal or baseline or are no longer considered clinically significant by the investigator or medical monitor. If clinically significant abnormalities do not return to normal/baseline within a time period judged reasonable by the investigator, the etiology should be identified, and the Sponsor notified.

Hematology:

Includes hemoglobin, hematocrit, white blood cell (WBC) and platelet counts, and WBC differential (neutrophils, bands, lymphocytes, monocytes, eosinophils, basophils, blasts). At times not designated in [Table 7](#), monitor CBC and WBC differential in accordance with institutional care

CONFIDENTIAL

Protocol KB-ENTO-3001 v4.0

(Amendment 3.0)

standards until ANC is $>1.0 \times 10^9/L$ or persistent leukemia is documented. Monitor platelet counts at times designated in [Table 7](#) and at other times, per institutional care standards until the platelet count is $>100 \times 10^9/L$ or persistent leukemia is documented. Monitor CBC and platelet count twice weekly during consolidation and at other times, as clinically indicated.

Clinical Chemistries:

Includes electrolytes (sodium, potassium, chloride, total CO₂ and/or bicarbonate, calcium, phosphate), liver function studies (AST, ALT, total and direct bilirubin), lactate dehydrogenase, alkaline phosphatase, blood urea nitrogen (BUN) or serum urea, creatinine, uric acid, glucose, amylase, and lipase. Include total creatine phosphokinase at Screening, Day 14 of each Induction cycle, and at the End of Study Treatment. At times not designated in [Table 7](#), monitor electrolytes, LFTs, BUN, creatinine, uric acid, and phosphate in accordance with institutional care standards until the risk of tumor lysis syndrome has abated. For subjects receiving nephrotoxic antimicrobial agents, closer monitoring of renal function throughout the period of hospitalization is recommended, consistent with institutional standards of care.

Coagulation Parameters:

Includes prothrombin time, activated partial thromboplastin time and international normalized ratio. Perform coagulation panel twice per week during induction. For subjects with evidence of disseminated intravascular coagulation, coagulation parameters including fibrinogen should be monitored until resolution.

Hepatitis/HIV Serologies:

Includes HBsAg, anti-HBs, anti-HBc, anti-HCV, and anti-HIV. Patients who are seropositive for HBsAg are excluded. HIV + patients may be considered for enrollment if they meet all criteria outlined in [Section 5.2](#) and for whom the risk of adverse interactions between anti-retroviral therapy and the study medication is assessed as minimal to none.

Urinalysis:

Includes dipstick evaluation for pH, glucose, protein, blood, leukocyte esterase and microscopic evaluation for red and white blood cells. After Screening, perform urinalysis as clinically indicated.

8.6.5 Pregnancy testing

A negative serum pregnancy test is required for female subjects (unless surgically sterile or postmenopausal) at Screening. Female subjects with medically documented ovarian failure must also have serum follicle stimulating hormone (FSH) levels within the institutional postmenopausal range at Screening. A urine pregnancy test will be performed for all females (unless surgically sterile or postmenopausal) on Day 1 of each cycle of induction and consolidation and at the End-of-Treatment evaluation.

CONFIDENTIAL

Protocol KB-ENTO-3001 v4.0

(Amendment 3.0)

8.7 Pharmacokinetic Assessments

Whole blood will be collected for measurement of plasma concentrations of ENTO at the following time points using a validated liquid chromatography mass spectrometry (LC-MS/MS) method:

Cycle 1 (Induction):

- Day 1, between 2 and 4 hours after study medication dose
- Day 7 predose only
- Day 14 predose and between 2 and 4 hours after study medication dose

Cycle 3 (Consolidation):

- Day 1 predose and between 2 and 4 hours after study medication dose
- Day 28-35 predose and between 2 and 4 hours after study medication dose

All predose samples must be obtained within 60 minutes before the first daily dose of study medication. The actual date and time (24-hour clock time) of each blood draw will be recorded.

Details concerning the processing and handling of PK samples, including labeling and shipping instructions will be provided in the Laboratory Manual.

8.8 Biomarker Assessments

Whole blood for biomarker testing will be obtained at the following time points:

- Screening,
- **Cycle 1 (Induction)**, Day 1 (pre- and 2 hours postdose), Day 7 and Day 14 (predose),
- Post-Chemotherapy Cycle 2
- **Cycle 3 (Consolidation)**, Day 1 (predose) and Days 28-35 (predose),
- At relapse, and
- End of Study Treatment.

All predose samples must be obtained within 60 minutes before the first daily dose of study medication. The actual date and time (24-hour clock time) of each blood draw will be recorded.

The extent of ENTO target engagement as measured by quantitation of pSYK and other phosphoproteins of interest as well as expression levels of relevant genes comparing baseline and on treatment blood samples will be explored. Additional targeted protein/phosphoprotein profiling (eg, pSYK expression) in leukemic cells specifically will be assessed at baseline. Biomarker assessments will also include baseline expression levels of *HOXA9/MEIS1* transcription factors and other relevant genes in leukemic cells from peripheral blood and bone marrow aspirate using standard expression profiling platforms (eg, Nanostring®) or next-generation sequencing. Mutational profiling in leukemic cells using standard platforms like next generation sequencing both at baseline and following study treatment will be explored. Results of all biomarker assessments will be evaluated for potential correlations with response and leukemic progression.

CONFIDENTIAL

Protocol KB-ENTO-3001 v4.0

(Amendment 3.0)

Details concerning the processing and handling of biomarker samples, including labeling and shipping instructions will be provided in the Laboratory Manual.

8.9 Pharmacogenomic Assessments

A whole blood sample will be collected at Screening for assessments of CYP2C9 and cytidine deaminase (the enzyme primarily responsible for cytarabine metabolism) polymorphisms. CYP2C9 polymorphisms will be evaluated in relationship to ENTO exposures (AUC, C_{max}) and as a potential covariate in population PK analyses. Cytidine deaminase polymorphisms will be evaluated for potential correlations with selected safety and efficacy outcomes. Examinations of selected germline genes implicated in leukemogenesis may be conducted for comparison with the corresponding genes in the leukemic clone.

8.10 Patient Reported Outcomes

Includes the European Quality of Life 5 Dimensions Questionnaire (EQ-5D-5L) and the European Organization for Research and Treatment of Cancer Quality of Life Questionnaire-Core 30 (EORTC-QLQ 30) collected at baseline, post-Chemotherapy Cycle 2, at End-of-Treatment and every 3 months thereafter until progression/relapse or death (whichever is earlier).

8.11 Adverse Events (AEs), Serious Adverse Events (SAEs), and Other Safety Reporting

Definitions for AEs and SAEs as well as methods for evaluating and reporting AEs and SAEs can be found in [Appendix 2](#).

8.11.1 Time Period for Reporting AEs and SAEs

During the period from signing informed consent for this study until initiation of study treatment, only SAEs will be reported. Beginning on Day 1 of Cycle 1 all AEs, and SAEs will be reported through 30 days after treatment completion. Thereafter, only SAEs that are study medication related as assessed by the investigator will be reported.

Prompt notification by the investigator to the sponsor of an SAE is essential so that legal obligations and ethical responsibilities are met. All SAEs will be reported to the sponsor or designee immediately, without undue delay, as outlined in [Appendix 2](#). The investigator will submit any updated SAE data to the sponsor immediately, without undue delay.

8.11.2 Method of Detecting AEs and SAEs

Care will be taken not to introduce bias when eliciting information on the occurrence of AEs and/or SAEs. Open-ended and non-leading verbal questioning of the participant is the preferred method to inquire about AEs. Investigators are not obligated to actively seek information on AEs or SAEs after the End-of-Treatment evaluation. However, if the investigator learns of any SAE, including a death, at any time after a subject has discontinued study treatment, and he/she considers the event to be reasonably related to the study medication or study participation, he/she must promptly notify the sponsor.

CONFIDENTIAL

Protocol KB-ENTO-3001 v4.0

(Amendment 3.0)

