All subjects who achieve morphologic CR, CRh, or CRi upon completion of Chemotherapy Cycle 2 may initiate or continue consolidation therapy in combination with ENTO or placebo (in accordance with their original randomized treatment assignment), as outlined in [Table 5](#) at the investigator's discretion either instead of or as a bridge to hematopoietic stem cell transplant.

Table 5: Treatment Phase –Consolidation

	Age < 60 years	Age \geq 60 years
Cytarabine	3.0 g/m ² , BID over 3 hours on Days 1, 3 and 5 every 28-35 days for up to 3 cycles*	1.5 g/m ² , BID over 3 hours on Days 1, 3 and 5 every 28-35 days for up to 3 cycles*

For subjects with < 5% residual blasts post-Induction Cycle 1, Consolidation Cycle 1 will consist of Chemotherapy Cycle 2. For patients with \geq 5% residual blasts post-Induction Cycle 1, Induction Cycle 2 ([Table 4](#)) will consist of Chemotherapy Cycle 2 with consolidation beginning thereafter. All subjects are eligible to receive up to 3 cycles of high dose cytarabine after Chemotherapy Cycle 2.

All subjects will undergo an End-of-Study Treatment Visit 30 ± 7 days after the last study treatment (either ENTO/placebo or chemotherapy, whichever is later) or prior to initiation of follow-on therapy (eg, maintenance therapy, HSCT), if sooner than 30 ± 7 days after last study treatment.

All subjects regardless of their post-remission status will be followed monthly for 3 months after the End-of-Study Treatment Visit and thereafter at least once every 3 months for progression/relapse, first salvage therapy, and survival until study termination. Unscheduled study visits at other time points are permitted in the setting of suspected leukemic recurrence or for evaluation and management of post-treatment sequelae.

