^b The following details minimally, regarding the diagnosis of AML will be collected and recorded on the eCRF: age and date of diagnosis (month, day, year); AML subtype (*de novo*; AML with myelodysplasia-related changes; therapy associated AML); history of myelodysplastic or myeloproliferative (eg, chronic myelomonocytic leukemia [CMML]) syndrome; history of prior exposure to leukemogenic agents (eg, alkylating agents, topoisomerase II inhibitors); cytogenetic abnormalities identified by conventional cytogenetic testing and/or FISH; complete blood count (CBC) with differential; percent blasts (peripheral blood and bone marrow); *NPM1* mutation subtype (A, B, D, other); *FLT-3* mutational status (wild-type; internal tandem duplication [ITD] mutation, tyrosine kinase domain [TKD] mutation, or both).

^c Vital signs include measurement of blood pressure, respiratory rate, pulse, temperature, and oxygen saturation level by pulse oximetry. After discharge from hospital, assess vital signs at each of the designated time points.

^d Perform a complete physical examination including neurological exam at Screening. After discharge from the hospital, a targeted physical exam may be performed at each of the designated time points. Subjects ≥ 60 years old receiving intermediate dose cytarabine or those with impaired renal function are at risk for cerebellar toxicity. Monitor for the occurrence of nystagmus, slurred speech, or dysmetria on each day of cytarabine dosing during Induction Cycle 2 and consolidation. Follow dose modification guidelines outlined in [Section 6.5.2](#) or in accordance with institutional care standards in the setting of neurotoxicity.

^e Height and weight will be measured at Screening. Only weight will be measured thereafter at designated time points.

^f ECG is required at Screening and thereafter as clinically indicated during treatment.

^g An echocardiogram (ECHO) or multi-gated acquisition (MUGA) scan must be performed at Screening and at the End-of-Treatment Visit. Consider repeating ECHO or MUGA within 48 hours prior to Induction Cycle 2 for subjects receiving anthracycline in Cycle 2 and at increased risk for cardiac toxicity.

^h Record all adverse events and concomitant medications through 30 ± 7 days after treatment completion. Thereafter, record only serious adverse events assessed as study medication related.

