- Morphologic relapse as defined by the reappearance of circulating blasts or $\geq 5\%$ blasts in the bone marrow not attributable to any other cause. *Note: In the setting of recent treatment, if there are no circulating blasts and the bone marrow contains 5 to 20% blasts, a bone marrow aspirate/biopsy should be repeated within 1 week to distinguish relapse from bone marrow regeneration.*
- Reappearance of cytologically or biopsy documented extramedullary disease, including new CNS disease or other new sites of extramedullary involvement. *Note: The reappearance of a cytogenetic or molecular abnormality would be considered a cytogenetic or molecular relapse. In the absence of morphologic relapse, this would not be considered a recurrence.*

Evaluation of response is recorded on the Response Assessment eCRF, and documentation of recurrence (relapse) is recorded on the Relapse Assessment eCRF.

Adverse Event

An AE is defined as any untoward medical occurrence in a clinical study subject, temporally associated with the use of study treatment, whether or not considered related to the study treatment.

Treatment-emergent Adverse Event (TEAE)

A TEAE is any adverse event beginning or worsening from C1D1 through 30 days following study treatment completion.

Treatment-emergent Laboratory Toxicity (TELT)

A TELT is a laboratory abnormality as defined in the National Cancer Institute - Common Toxicity Criteria for Adverse Events (NCI-CTCAE) v5.0 (NCI 2017, which occurs on or after the start of study treatment and up to 30 days following discontinuation of all study treatment and is at least 1 grade shift from the baseline value. TELTs are determined programmatically from laboratory assessments recorded in the relevant CRF pages.

Concomitant Medications

Concomitant medications are those medications taken on or after the initiation of study treatment. This includes medications started prior to the initiation of ENTO/placebo and continued after the initiation of ENTO/placebo. These medications will be recorded in the Prior and Concomitant Medications page of the CRF.

Prior Medications

Prior medications are those medications taken and discontinued prior to the initiation of study treatment. These medications will be recorded in the Prior and Concomitant Medications page of the CRF.

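### Sites may stop asking about new adverse events at the End-of-Treatment visit, which can precede Day 30, while TEAEs are counted to a fixed Day 30 and not separated at the start of follow-on therapy

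*Protocol*

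**What the plan says.** Days below are counted from the last study treatment.

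- **Reporting period.** Protocol 8.11.1: "Beginning on Day 1 of Cycle 1 all AEs, and SAEs will be reported through 30 days after treatment completion". Only after that does the duty narrow to SAEs related to study medication.
- **Recording period.** Protocol Table 7, footnote h: "Record all adverse events and concomitant medications through 30 ± 7 days after treatment completion".
- **Active questioning.** Protocol 8.11.2: "Investigators are not obligated to actively seek information on AEs or SAEs after the End-of-Treatment evaluation".
- **When that evaluation happens.** Protocol 4.1: "All subjects will undergo an End-of-Study Treatment Visit 30 ± 7 days after the last study treatment", "or prior to initiation of follow-on therapy (eg, maintenance therapy, HSCT), if sooner than 30 ± 7 days after last study treatment". No lower limit in days is given for the early route.
- **After that visit.** The adverse-event row of Table 7 has no mark under long-term follow-up. Footnote x limits the later contacts to relapse or progression, first salvage therapy and survival.
- **What is counted.** SAP 4.4.4: "A TEAE is any adverse event beginning or worsening from C1D1 through 30 days following study treatment completion". Protocol 9.4.4 uses the same window. SAP 4.4.4 defines study treatment as the blinded drug and/or the protocol chemotherapy. Neither document ends the count, or marks events, at the start of HSCT, maintenance or salvage.
- **How it is shown.** SAP 6.5.1 summarises TEAEs by treatment group, with separate summaries of serious, fatal and study-medication-related TEAEs.

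**The concern.** A TEAE percentage is comparable across subjects only if events were looked for over the window in which they are counted. Here a new event can be reportable and countable on a day when nobody is required to ask about it. How long that stretch lasts depends on when the subject moves to other treatment.

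The early visit is a foreseen path. Section 4.1 allows consolidation as a bridge to transplant, and Section 7.1 makes both HSCT and failure to reach CR, CRh or CRi reasons to stop study medication.

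A second problem acts in the other direction. If a subject starts conditioning, maintenance or salvage inside the 30 days and an event is reported, it enters the TEAE tables alongside events from before the switch, although another treatment may have caused it. The all-cause and serious TEAE summaries, which support the safety objective, carry both effects.

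**Working it through.** The plan states no figure on this point, so there is none to reproduce. The check is window arithmetic plus a comparison of the rules.

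**Inputs**
- Length of the reporting and TEAE window: 30 days (protocol 8.11.1 and 9.4.4; SAP 4.4.4).
- Routine visit window: 30 ± 7 days (protocol 4.1), that is 30 − 7 = Day 23 to 30 + 7 = Day 37.
- Early visit: any day before follow-on therapy (protocol 4.1). The example days below Day 23 are assumptions.

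**Step 1. Days in which new events need not be asked about** = max(0, 30 − visit day).

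| Visit day | Days not asked about | Share of 30 |
|---|---|---|
| 30 to 37 | 0 | 0% |
| 23 | 7 | 23% |
| 14 | 16 | 53% |
| 10 | 20 | 67% |
| 7 | 23 | 77% |
| 1 | 29 | 97% |

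**Step 2. One event under each rule.** Take a subject seen on Day 23 who has a new event on Day 27. Section 8.11.1 requires it to be reported. Protocol 9.4.4 and SAP 4.4.4 count it. Section 8.11.2 does not require anyone to ask about it, and Table 7 schedules no later adverse-event collection. Footnote h does not settle the matter, because its ± 7 can be read as closing recording on Day 23.

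**Step 3. Does this separate the arms?** Let f be the share of an arm starting follow-on therapy, all at Day 10, with no gap for anyone else (assumptions). Mean days not asked about = f × 20.

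| f, ENTO vs placebo | Mean days, ENTO vs placebo | Difference |
|---|---|---|
| 20% vs 20% | 4.0 vs 4.0 | 0 |
| 10% vs 30% | 2.0 vs 6.0 | −4.0 |
| 30% vs 10% | 6.0 vs 2.0 | +4.0 |
| 0% vs 40% | 0 vs 8.0 | −8.0 |

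The documents give no value of f for either arm, so the sign and size cannot be derived from them. Under-detection lowers an arm's count and events from the next treatment raise it, so even a known f would not fix the net direction.

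**Step 4. Can an existing contact close the gap?** Follow-up is monthly for three months after the visit. Taking a month as 30 days, the first contact falls near Day 53 after a Day 23 visit (23 + 30), Day 40 after a Day 10 visit and Day 31 after a Day 1 visit. All are past Day 30, so one question there covers the whole gap.

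**Step 5. Scale in the study as it ended.** SAP 4.2 gives 15 randomized subjects. If they split 8 and 7 (assumption), one subject moves an arm's percentage by 1/8 = 12.5 or 1/7 = 14.3 points.

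**The case against.** The case on the other side is substantial, and much of it stands.

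- **Reporting does not stop at the visit.** Section 8.11.1 keeps the duty to report every adverse event to Day 30, related or not, and 8.11.3 requires follow-up of events already reported. Section 8.11.2 removes an obligation to ask; it does not forbid asking. A reader might infer that after the visit sites owe only related SAEs that they happen to hear of. Up to Day 30 that is not so. What lapses is required questioning about new events.
- **Footnote h may just restate the visit tolerance** around the same nominal 30 days. That is a fair reading. It is wording to align, hardly a separate window.
- **Deaths are unlikely to be missed.** Survival is followed monthly after the visit, and a death within 30 days is reportable. Fatal TEAEs are the summary least affected by under-detection.
- **A fixed 30-day window is a legitimate choice**, and the plan has a related-TEAE summary, a causality assessment that weighs concomitant therapy, and listings. This stands in part. A window that ignores later therapy needs equal questioning after the switch, which 8.11.2 does not secure. The related summary rests on investigator attribution and leaves the all-cause and serious summaries mixed.
- **Both blinded arms have the same rules.** This stands: bias between arms requires a difference in the rate or timing of follow-on therapy.

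A reader might also infer a size for that bias from the sample-size assumptions: CR of 87% vs 70% leaves 13% vs 30%, and at an assumed Day 10 switch 0.13 × 20 = 2.6 and 0.30 × 20 = 6.0 days. The documents do not support this. Section 7.1 requires stopping only without CR, CRh or CRi, and 4.1 lets CRh and CRi subjects continue, so the complement of a CR rate is not the share who must stop. The two rates are also not like for like: 87% matches 13 of 15 subjects with CR or CRi in Section 2.2, while 70% is a CR rate (9.2). The complement also includes early deaths, who start no salvage.

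**Conclusion.** The point holds as a mismatch between ascertainment and counting. Required questioning can end before the TEAE window does: by 7 of 30 days (23%) after a Day 23 visit, which follows from the documents alone, and by more after an earlier visit (20 of 30 at an assumed Day 10). TEAEs that start after follow-on therapy begins are not distinguished. Salvage is not named in the visit rule in 4.1; treating it as follow-on therapy is a reading of an open list of examples.

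The consequence shown is unequal ascertainment between subjects. A between-arm bias is possible but conditional, with unknown net direction and no rates in the documents from which to size it.

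For the protocol as designed, the change is worth making because it is cheap. For the study as it ended the effect is small and descriptive only: 15 subjects and no formal testing (SAP 4.1, 4.2). It is not nil, because the SAP now exists mainly to produce safety tables and a single event is visible in a percentage.

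**What to change.** 1. **Protocol 8.11.2 and Table 7.** In 8.11.2, replace 'after the End-of-Treatment evaluation' with 'after 30 days following the last dose of study treatment'. Set footnote h to 30 days so that it agrees with 8.11.1.
2. **Protocol follow-up.** At the first monthly contact already scheduled, ask about adverse events up to Day 30 and record the start date of any follow-on therapy.
3. **SAP 4.4.4 and 6.5.1.** Flag TEAEs with onset on or after the start of HSCT, maintenance or salvage, and show the TEAE summaries with and without them.

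Cost: wording changes, a few minutes at an existing contact, and one more table split. The question in step 2 relies on recall over roughly a month, which is weaker than a Day 30 visit but better than no required question.

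For the terminated study, steps 1 and 2 come too late. What remains is the flag in step 3 and a sentence in the clinical study report stating the ascertainment limit. First salvage therapy is already followed; whether HSCT and maintenance start dates were captured should be confirmed before database lock.
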